This parametric comparative trial will randomly assign 140 inner-city adolescents with ADHD to (1) CASH-AA Only or (2) CASH-AA + MIP. Treatment will occur in community behavioral health clinics. All participants will receive behavioral interventions (CASH-AA): family psychoeducation in ADHD symptoms, executive functioning, and developmental impacts; family-based motivation and ADHD accommodation interventions; and academic training focused on home environment support and organizational skills. Half of the participants

will also receive medication decision-making interventions (MIP): ADHD medication psychoeducation, family decision-making interventions, and (for those who elect to start medication) coordinated medication management. Half of the sample will have comorbid substance use problems. Treatment will occur in three community clinics; therapists will be randomly assigned to study condition. Caregivers and adolescents will complete assessments at baseline, 3, 6, and 12-month follow-up. Multilevel modeling will compare the effectiveness of each condition on key patient and service use outcomes. Patient-centered analyses will explore differential treatment effects based on (a) Medication decision (yes/no); (b) Substance use comorbidity (yes/no); (c) Race/Ethnicity (Hispanic, African American).

Quantitative outcome analyses will test for service use effects, symptom reduction, and quality of life improvements that are primary reasons for seeking clinical services. Qualitative interviews will document family-specific rationale for decisions about medication, compliance with behavioral and medication interventions, and suggestions for improving services and service integration. Note that families assigned to CASH-AA Only will retain the option of pursuing ADHD medication through treatment-as-usual procedures at their respective clinic. Similarly, families assigned to CASH-AA + MIP will not be required to start ADHD medication. Instead, they will receive informed-choice interventions and can choose when and if to start medication; the study will assess the impact of these decisions on clinical outcomes.

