intensive family engagement and family-agency coordination efforts to help families overcome barriers to enrolling in services, procedures especially valuable for enrolling hard-to-engage families. Linking procedures will cease upon completion of the first intake interview (after which randomization will occur). After linking is completed, research staff will maintain contact with families solely to complete follow-up interviews, which will occur with every randomized family regardless of treatment attendance.

Randomization to study condition and therapist assignment. Cases will be randomly assigned to study condition after completing an intake interview at the assigned site. Urn randomization will promote balance between conditions on 3 variables: sex, ethnicity (Hispanic, African-American, Other), and ASU problems (Yes, No). Once randomized, cases will be assigned to a study therapist in alternate turns. Note that in some sites, it will be necessary to follow “nearly random” assignment to condition, if the given site assigns cases to clinicians based on a shared rotation of case assignment. That is: Any given case is assigned to the next available clinician in the duty rotation, or, the clinician who is on duty during the given intake appointment. Treatment site therapists who agree to participate as study therapists will be consented in their private offices by research staff. We anticipate some degree of therapist dropout due to staff turnover during two years of enrolling study cases. When a study therapist drops out in either condition, the given site will be asked to nominate two potential replacements, and the new therapist will be randomly selected from that pair. All partnering treatment sites will be in close proximity to assigned study participants and easily accessible via public transportation. Each site will routinely prescribe weekly treatment sessions and offer in-house psychiatric support for all cases. All therapists at each site who treat adolescent clients and who volunteer to participate will be accepted into the study randomization pool.

Study Conditions

Behavioral Only Condition: Changing Academic Support in the Home for Adolescents with ADHD (CASH-AA)

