As occurred during the pilot tests of the MIP and CASH-AA protocols, the proposed study will provide on-site training in CASH-AA (3 hours) to all study therapists, led by study investigators. Study investigators will then continue training therapists in the Integrated condition in MIP (additional 3 hours). After initial training, two separate monthly fidelity monitoring meetings will occur at each site, one for each study condition. Ad hoc training will be provided to new therapists whenever there is staff turnover.

Fidelity monitoring (FM) meetings will be organized using principles of localized quality assurance procedures for promoting the sustainability of evidence-based practices in usual care. Specifically, FM meetings will feature data from the therapist-report CASH-AA and MIP fidelity measures, along with a therapist-report measure of evidence-based practices for adolescent

conduct and substance use problems, as quality assurance tools and clinical supervision aids. Also, over the course of the study FM meetings will follow a multistep process to develop on-site clinical expertise and incrementally increase on-site supervision responsibilities in proportion to decreased extramural involvement.

Study Measures

Client Demographics, Multidomain Risk Factors, and Psychiatric Diagnoses

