measure. Also, phone screening data from the engaged versus non-engaged samples will be compared to test for significant differences in demographic or family characteristics.

Analytic Strategy to Account for Nesting Effects

The proposed study has a nested design: clients are nested within therapists, and therapists are nested within treatment sites. In a nested design, the application of a standard fixed effects GLM typically produces biased inferential tests because the error terms of units within each level are often correlated. We will use multilevel modeling with random effects that includes the sandwich estimator to adjust parameter estimates and standard errors for nested structure. This approach is used to analyze nested data when the goal is to examine outcome effects at the level of the individual (i.e., client), and the hierarchical structure of the data (i.e., client nesting at therapist level) is akin to a nuisance factor to be accounted for, but inference about the degree of correlation is not of interest. Also, the design is nested at the level of treatment site: therapists are nested within site. Recommendations stipulate that 10-20 sites are needed to produce stable estimates for random effects modeling. Because this study will include only four sites, we will adopt the typical alternative of modeling site as a fixed effect included as a nuisance covariate in analyses. This approach is the norm for multisite studies in behavioral sciences whenever there is a small number of participating sites. If the fixed effect of treatment site is significant for any given client outcome analysis, we will re-conduct the given analysis using a within-site approach; due to small sample size this would be considered an exploratory analysis.

Plan of Analysis for Main Outcomes: Aims 1 & 3

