LGC will proceed using Mplus version 7, as follows. First, we will test a series of growth curve models for each outcome, representing three forms of growth (no change, linear change, quadratic change), to determine the overall shape of the individual change trajectories; overall model fit will be evaluated by examining the chi-square, RMSEA, CFI, and TLI indices. Second, we will test unconditional models for all outcomes to obtain the average effect for change over time in outcome, without including treatment condition or other covariates. Third, we will add the two predictors, Condition (Behavioral Only vs. Integrated) and baseline Substance Use (SU+ vs. SU-) to the models in order to test the impact of each predictor on initial status and change over time. We will also test Condition X SU interactions, and if any are significant for a given outcome, we will re-run that model separately for the SU+ and SU- participants to test simple effects. Treatment effects (Aim 1) for any given outcome will be shown by a statistically significant effect parameter, as tested by the pseudo z test—calculated by dividing the coefficient by its standard error—associated with Condition. Heterogeneity of Treatment Effects (HTE; Aim 3) for any given outcome will be identified by a significant effect for the Condition X SU interaction term; post-hoc analyses will be used to explore these interactions to determine whether Integrated effects appeared to be stronger or weaker in SU+ versus SU- cases. Initially, all models will be adjusted for nuisance covariates: sex, age, and ethnicity; family income; caregiver education level; and treatment site. We will then further explore HTE (Research Question 1) by testing for outcome differences based on age, ethnicity, and sex subgroups. Per above we will use the sandwich estimator to control for therapist nesting. Effect size estimates for significant findings in Aims 1 and 3 analyses will be calculated based on Feingold's procedures for calculating effect sizes for LGC analyses. Also, for any outcome that deviates substantially from normality—typical for delinquency and SU data—we will use two-part growth curve models, which allow for the simultaneous estimation of separate but correlated continuous and categorical LGC models. Two-part models are used when a large number of participants report the absence of the given variable (i.e., no delinquent activities or SU), resulting in highly skewed data. In two-part models, the original distribution of the outcome is separated into categorical and continuous parts, each modeled by separate but correlated growth functions. In the categorical part, a binary indicator variable is created to indicate any vs. none of the outcome in question. The continuous part models the frequency of occurrence of the outcome given any positive occurrence.

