
Finally, for Research Question 2 pertaining to Individual Differences, we will use methods in which days of ADHD medication use since study entry is positioned as a predictor of client outcomes. Because medication use will be dependent on client choice and not randomly assigned, the first step is to create 2 new groups: High Use vs. Low/No Use (or 3 groups, depending on data distributions). This will be done via propensity score matching analyses for ordinal treatment variables. Propensity scores will be calculated using an ordinal logit model to represent each client's probability to be medicated over time as a function of multiple baseline variables presumed to influence medication choice (condition, demographics, ADHD symptom severity, comorbid symptoms). Clients will be matched on these variables to minimize differences in propensity scores and maximize differences in medication use days at 12-month FU. This will statistically control for observed variables that might influence the likelihood of natural selection into medication use over time. Once propensity score-based groups are created, we will conduct matched-pair analyses for each outcome, using dependent *t*-tests for continuous and McNemar's chi-square test for dichotomous variables⁷⁸.

Plan of Analysis for Main Outcomes: Aim 2

Multilevel modeling will examine Condition effects on time-invariant client outcomes: treatment attendance, medication acceptance, and client satisfaction (averaged across caregiver and adolescent); separate models will be run for each variable. Outcomes will be analyzed using multilevel regression analysis with random intercepts and slopes in Mplus version 7. Condition will be entered as a level-1 predictor and regressed directly on the outcome variable; the influence of the predictor is examined by testing the significance of the effect parameter. As discussed above, to control for therapist nesting effects we will use the sandwich estimator; all models will be adjusted for the nuisance covariates listed above; and missing data will be handled with robust maximum likelihood estimation (see below).

Analytic Plans for Missing Data

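### Condition varies only between therapists, yet it is tested with a therapist sandwich and a z reference with no small-sample correction stated; with 12 to 40 therapists a nominal 5% test would reject in about 9-20% of null trials

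*Combined protocol and SAP*

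**What the plan says.** **Who carries Condition.** Study Design and the Project Abstract have therapists randomised to condition within site. In Therapist Training and Fidelity Monitoring Procedures everyone is trained in CASH-AA, and the investigators then "continue training therapists in the Integrated condition in MIP"; monitoring meetings are held separately by condition. Under Randomization to study condition and therapist assignment, "Once randomized, cases will be assigned to a study therapist in alternate turns". Where a site uses a duty rotation, the clinician on rotation determines the condition, which ties it to the therapist even more directly.

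**How Condition is tested.** In Plan of Analysis for Main Outcomes: Aims 1 & 3, an Aim 1 effect "will be shown by a statistically significant effect parameter, as tested by the pseudo z test", defined as the coefficient over its standard error. The same section adds: "Per above we will use the sandwich estimator to control for therapist nesting". For Aim 2, Condition is a level-1 predictor in a "multilevel regression analysis with random intercepts and slopes in Mplus version 7", and "to control for therapist nesting effects we will use the sandwich estimator". No reference distribution is given there.

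**Few clusters.** Analytic Strategy to Account for Nesting Effects addresses small numbers for sites only: "Because this study will include only four sites, we will adopt the typical alternative of modeling site as a fixed effect". The Project Abstract gives a different count: "Treatment will occur in three community clinics; therapists will be randomly assigned to study condition". The number of therapists, the therapist ICC and the significance level are not stated.

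**The concern.** Because no therapist delivers both arms, the information on Condition accrues between therapists. A cluster sandwich relies on a large number of clusters. With few, its standard error is too small on average and itself variable, so 1.96 is too low a cut-off. The plan removes site as a random factor because there are few sites, but makes no check on the number of therapists, who are the units that carry the comparison.

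At stake are the tests of Condition in Aims 1 and 2 and, to a lesser degree, the Condition x substance use (SU) interaction used for heterogeneity in Aim 3. A false difference would be declared at roughly two to four times the intended rate, about half of the time in favour of Integrated. Research Question 2 uses matched-pair tests and is outside this point.

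The level-1 label for Condition in Aim 2 is not the cause, and relabelling alone would not restore the error rate. Separately, the Aim 2 text does not say which slopes are random. If a random Condition slope across therapists is meant, it cannot be estimated, since each therapist has a single value of Condition.

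**Working it through.** The plan states no error rate or power calculation, so there is no figure of its own to reproduce.

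**Inputs from the document:** 140 clients, half per arm; three or four sites as fixed effects; baseline, 3, 6 and 12 months; 10-15% missing outcome data (12.5% used); adjustment for sex, age, ethnicity, income, caregiver education, site and baseline SU; therapist sandwich; z.

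**Assumptions:** two-sided 5%; therapist ICC 0.05; K therapists. Taking turns suggests at least two therapists per arm per site, so K = 2 x 2 x 3 = 12 or 2 x 2 x 4 = 16 is the low case. Turnover could raise it, and 40 is taken as a high case. K = 8 (one per arm in each of four sites) is shown only as an extreme.

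**Step 1: closed form for the simplest case.** Take equal caseloads, therapist means as data, Condition and S site effects fitted, and no client covariates. The true variance of the Condition estimate is 4σ²/K. The sandwich gives (4/K²) x (residual sum of squares), with expectation (4σ²/K) x (K − S − 1)/K. Hence z = t x √[K/(K − S − 1)], with t on K − S − 1 df, and

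null rejection = P(|t on K − S − 1 df| > 1.96 x √[(K − S − 1)/K]).

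For K = 16, S = 4: df = 11, √(11/16) = 0.829, effective cut-off 1.96 x 0.829 = 1.625, rejection 13.2%. Correcting the size of the standard error but keeping 1.96 would still give P(|t on 11 df| > 1.96) = 7.6%. Both the standard error and the reference distribution contribute.

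**Step 2: the planned form.** Four-wave linear growth model; intercept and slope regressed on Condition, SU, Condition x SU, the listed covariates and site; no treatment effect; 5000 trials per cell. Entries are null rejection (%) for the effect on slope with |z| > 1.96, equal / unequal caseloads.

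| Therapists, sites | Closed form | Condition | Condition x SU |
|---|---|---|---|
| 8, 4 (extreme) | 31.6 | 31.5 / 31.5 | 14.9 / 14.8 |
| 12, 3 | 14.8 | 15.1 / 19.7 | 11.9 / 13.2 |
| 16, 4 | 13.2 | 15.0 / 17.4 | 9.9 / 10.9 |
| 24, 4 | 9.7 | 10.9 / 13.4 | 9.0 / 9.6 |
| 32, 4 | 8.3 | 9.3 / 11.6 | 7.8 / 9.5 |
| 40, 4 | 7.5 | 8.8 / 10.7 | 7.3 / 8.6 |

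Monte Carlo error is about ±0.8 points near 9% and ±1.1 near 20%. A separately coded growth simulation (1000 trials per cell, error about ±1.8 to ±2.5 points) gave 15.7/20.8, 13.5/15.2, 10.3/12.7 and 9.0/10.6 for 12 (three sites), 16, 24 and 40 therapists.

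**Step 3: Aim 2 form** (one time point, 4000 trials, z assumed): 15.8/20.3 for 12 therapists in three sites, 14.5/17.1 for 16, 10.8/15.2 for 24, 10.2/12.1 for 32 and 9.0/10.9 for 40.

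**Step 4: what drives it.** With complete data and equal caseloads, moving the ICC from 0 to 0.10 changes rejection only from 13.0% to 15.0% at 16 therapists and from 8.0% to 9.4% at 40. A small therapist effect is therefore no protection. Adding a therapist random intercept while keeping the sandwich and z still gave 13.7% at 16 and 8.0% at 40 with equal caseloads. Site effects and covariates matter: without them, rejection is about 11-12% at 12 therapists and 7% at 40, but the plan specifies them.

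**Step 5: what restores 5%.**
- CR2 with Satterthwaite df: 4.2-6.3% for Condition in the growth model. In the one-time-point model, 4.9-6.1% for Condition and 4.2-5.3% for Condition x SU.
- Therapist-mean slopes with t on K − S − 1 df: 3.8-5.6% (Condition only).
- Not enough: a G/(G − 1) factor with t on G − 1 df, where G is the number of therapists. In the one-time-point model this leaves Condition at 10.4/13.2% with 16 therapists and 7.8/9.0% with 40.

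**The case against.** The size rests on inputs that the document does not give. Therapist count, ICC and significance level are all assumed, and nothing caps the count at 40: every eligible volunteer enters the pool and leavers are replaced over two years. The 20% end needs 12 therapists, three sites and unequal caseloads, whereas the analysis section plans four sites and taking turns suggests fairly even caseloads. The plan states no correction but does not exclude one, and z is explicit only for Aim 1. The 10-20 guideline quoted for sites concerns stable random effects, not the validity of a sandwich. Two-part and quadratic growth models were not simulated, and Kenward-Roger was not tried.

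Most of this stands as a limit on the figure, not as an answer to the point. The rate is conditional on the therapist count, and 9-15% (16 to 40 therapists, four sites, equal caseloads) is the more typical range. Larger counts shrink the inflation without removing it: at 64 therapists, about 140/64 = 2.2 clients each, the growth model still rejects in 7.6% (equal) and 8.0% (unequal) of null trials. Silence on a correction cannot be read as a plan to use one when the stated criterion is coefficient over standard error referred to z.

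**Conclusion.** The concern holds. Followed as written, the Aim 1 test of Condition does not keep a 5% error rate for any therapist count examined. For 12 to 40 therapists the null rejection rate is about 9-20%, roughly two to four times nominal. Condition x SU is inflated to about 7-13%. Aim 2 behaves the same way if its unstated reference is also z. These figures assume a two-sided 5% level, an ICC of 0.05 (of little influence), the planned site effects and covariates, and a linear growth model. The therapist count matters most, and its absence from the plan is part of the defect. The size is unknown for two-part models. This should be fixed, and the fix lies in the analysis plan.

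**What to change.** 1. State the planned number of therapists per arm and site, and reconcile three clinics (Project Abstract) with four (Study Purpose And Aims; Analytic Strategy to Account for Nesting Effects). Both set the degrees of freedom.
2. Define Condition as a therapist-level fixed effect with no random Condition slope, and name the slopes that are random.
3. For Condition and Condition x SU in Aims 1 to 3, leaving Research Question 2 aside, replace the z test with a CR2 sandwich and Satterthwaite df, or a therapist random-intercept model with Kenward-Roger or Satterthwaite df. CR2 is the option checked here. For Condition alone, a therapist-level t test with df = therapists − sites − 1 also works.
4. Name the reference distribution for Aim 2, and say how the two-part models will be handled. Check the error rate of the chosen method there before relying on it.

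**Cost.** Conduct does not change. Critical values rise above 1.96: for the therapist-level t, 2.31 (12 therapists, three sites, 8 df), 2.20 (16, four sites, 11 df), 2.09 (24, 19 df) and 2.03 (40, 35 df). P-values will be less favourable and some power is lost; the loss was not quantified. The plan commits client-outcome analyses to Mplus, and the corrected tests may need other software.

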The proposed study will help fill this alarming gap in the evidence base for adolescents with ADHD. The study is significant for several reasons. It will occur in existing behavioral health clinics to test front-line treatment effectiveness. Both protocols (CASH-AA and MIP) are evidence-based, affording a rigorous test of the best available treatment options for this clinical group. The test has immediate real-world implications: Families enrolled in specialty treatment settings invariably prefer behavioral services only, but they need to know whether integrated medication interventions can provide a meaningful boost to outcomes that are most important to them. Importantly, whereas ethnic minorities and also girls with are severely underserved and under-researched, the current study will focus on urban minority teens, and about half the sample will be female. Also, this study will be among the first to test evidence-based ADHD treatment options for adolescents who use substances, another significantly underserved and high-priority clinical risk group.

This comparative trial will randomly assign 140 adolescents with ADHD to Behavioral Only (containing CASH-AA) or Integrated (containing CASH-AA + MIP) treatment. The CASH-AA and MIP protocols will be incorporated in existing services in four clinics that support both study conditions. Adolescents and caregivers will complete research interviews at baseline and 3, 6, and 12-months follow-up. Multilevel modeling will compare conditions on symptom, quality of life, and service use outcomes and also test patient-centered heterogeneity of treatment effects and individual difference effects. Semi-structured interviews will document

family-specific rationale for decisions about initiating and continuing in behavioral and medication interventions, along with suggestions for improving the respective treatment services. The study has three specific aims:

Aim 1: Comparative Impact on Client Functioning

Hypothesis 1: Reduced Symptoms. Integrated clients will show greater decreases in ADHD symptoms (inattention, hyperactivity/impulsivity) and comorbid problems (conduct problems, drug use) than Behavioral Only clients.

Hypothesis 2: Improved Quality of Life. Integrated clients will show greater improvements in executive functioning (self-regulation, self-organization) and school functioning (grades, attendance, motivation) than Behavioral Only.

Aim 2: Comparative Impact on Service Utilization

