Hypothesis 3: Better Treatment Attendance. Integrated clients will attend more behavioral therapy sessions and medication management sessions than Behavioral Only clients.

Hypothesis 4: Greater Medication Acceptance and Treatment Satisfaction. Integrated clients will more often consent to medication, show greater medication compliance, and report greater overall satisfaction than Behavioral Only.

Aim 3: Examine Patient-Centered Outcomes

Research Question 1: Heterogeneity of Treatment Effects. Will clients with co-occurring substance use problems have worse treatment outcomes than those without? Will there be outcome differences based on age, ethnicity, sex?

Research Question 2: Analysis of Individual Differences. Across treatment conditions, will clients who choose to start a medication regimen have better treatment outcomes than those who do not?

Study Design

This study emphasizes ecological validity: Both protocols will be implemented in existing outpatient behavioral services by agency clinicians. To promote internal validity, randomization will occur within site at both the client and therapist level (i.e., study therapists at

each site will be randomly assigned to condition). The primary benefit of “doubly randomized” designs is that they minimize potential bias related to site effects—because randomization occurs within each site—and therapist sampling bias—because therapists are randomly assigned to condition. The use of a Behavioral Only condition will control treatment expectancy effects. Therapists will be trained and supervised to implement CASH-AA and MIP as part of their otherwise routine duties; that is, the protocols will be additional components of their usual practice for study cases. To maximize protocol exposure, and to promote consistency in the timing of protocol implementation across conditions and cases, therapists will be asked to implement CASH-AA and MIP at the start of treatment (unless contraindicated).

Note: (1) ADHD medication will be available to all Behavioral Only cases via routine site practices for ADHD treatment; and (2) MIP supports family decision-making about medication but does not require families to start a medication regimen.

Sample Description

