Study eligibility criteria will be: (1) Adolescent age 12–18; (2) Primary caregiver able to participate in treatment; (3) Adolescent meets DSM-5 diagnostic criteria for ADHD; (4) Adolescents who use substances (estimated 20-50% of sample) meet ASAM criteria for non-intensive outpatient services; (5) Adolescent not enrolled in any other behavioral treatment; (6) Caregiver expresses desire, and adolescent expresses willingness, to participate in outpatient treatment; (7) Family has health benefits that meet the requirements of study treatment sites, all of which accept a broad range of insurance plans including Medicaid. Exclusion criteria will be: mental retardation or autism-spectrum disorder; medical/psychiatric illness requiring hospitalization; current psychotic symptoms; active suicidal ideation; severe substance use problems that require immediate relief (detox or residential placement).

The study sample will be drawn from similar referral streams to those that produced cases for the recently completed CASALEAP RCT and the CASH-AA and MIP pilot studies, as well as from the existing clinical referral stream of each treatment site. Thus the following projections for study demographic and psychiatric characteristics are based on data from those affiliated studies. Participants will include both males (52%) and females and averaged approximately 15.7 years of age (SD = 1.5). Self-reported ethnicities will be Hispanic (59%), African American (21%), multiracial (15%), and other (6%). Households will be headed by a

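### Effect modification by age is to be explored in unspecified age subgroups, with no Condition × age term, although age is available as a number; grouping it would lose information to a degree set by cut points not yet chosen.

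*Combined protocol and SAP*

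**What the plan says.** Aim 3, Research Question 1 (Study Purpose And Aims) asks: "Will there be outcome differences based on age, ethnicity, sex". The method is in Data Analysis, Plan of Analysis for Main Outcomes: Aims 1 & 3, which takes heterogeneity further by "testing for outcome differences based on age, ethnicity, and sex subgroups". That sentence is the whole specification for age. It gives no cut point, number of groups or model term.

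Just before it, the same section states: "Initially, all models will be adjusted for nuisance covariates: sex, age, and ethnicity; family income; caregiver education level; and treatment site". Age is thus a covariate in the growth models, but its coding is not given. The only interaction with Condition that is written out is the one with baseline substance use.

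Sample Description sets the eligible range ("Adolescent age 12–18") and projects a mean age of 15.7 years with SD 1.5, so age is available as a number. Age is not one of the three urn-randomization variables (sex, ethnicity, substance use problems), so the design supplies no age strata. The Project Abstract's list of patient-centered analyses names medication decision, substance use comorbidity and race/ethnicity, and does not mention age.

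**The concern.** An analyst who follows the text has to turn a numeric variable into groups, and the plan does not say how. Two things follow.

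- **The cut is open.** It could be settled after the data are seen, and the question is asked of several outcomes: ADHD symptoms, conduct problems, substance use, executive functioning and school functioning. A finding that outcomes differ by age could then depend on where the line was drawn.
- **Grouping discards information.** It treats clients just either side of a cut as different and all clients within a group as the same. With 140 clients randomized, a test of effect modification is already imprecise.

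There is also a more basic gap. The sentence speaks of outcome differences under a heterogeneity label. Without a Condition × age term, a reader cannot tell whether the test concerns age as a predictor of outcome or age as a modifier of the treatment effect. Only the second is heterogeneity of treatment effect.

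**Working it through.** The documents state no power, alpha or information figure for this analysis, so there is nothing of the plan's own to reproduce. The check asks how much information on a linear Condition × age effect survives grouping.

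**Inputs from the documents:** mean 15.7, SD 1.5 and range 12–18 (Sample Description); 140 randomized, half to each condition.

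**Assumptions:** age is normal(15.7, 1.5) limited to 12 up to the 19th birthday, which gives mean 15.675, SD 1.401 and variance 1.962; effect modification is linear; residual variance is equal.

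**Formula.** Information kept = between-group variance of age ÷ total variance of age. For two groups with shares p and 1−p this is r² = p(1−p)(difference in group mean ages)² ÷ 1.962. The standard error is multiplied by 1/√r², and the equivalent sample size is 140 × r².

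**Two groups**

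| Cut | Share below | Mean ages | r² | Lost | SE factor | 140 × r² |
|---|---|---|---|---|---|---|
| 14 | 0.124 | 13.35, 16.01 | 0.392 | 61% | 1.60 | 55 |
| 15 | 0.320 | 14.08, 16.43 | 0.611 | 39% | 1.28 | 86 |
| 15.7 | 0.504 | 14.54, 16.82 | 0.661 | 34% | 1.23 | 92 |
| 16 | 0.585 | 14.73, 17.01 | 0.647 | 35% | 1.24 | 91 |
| 17 | 0.817 | 15.22, 17.70 | 0.467 | 53% | 1.46 | 65 |

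Example, cut at 15: 0.320 × 0.680 × (16.426 − 14.080)² ÷ 1.962 = 0.611.

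**Three groups**

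- Cuts at 15 and 17: shares 0.320, 0.497, 0.183; means 14.08, 15.96, 17.70. Between-group variance = 0.815 + 0.040 + 0.748 = 1.603. Kept: 1.603 ÷ 1.962 = 0.817, so 18% is lost.
- Cuts at 14 and 16: shares 0.124, 0.460, 0.415; means 13.35, 15.10, 17.01. Between-group variance = 0.673 + 0.154 + 0.742 = 1.568. Kept: 0.799, so 20% is lost.
- Equal thirds: 18% lost.
- A wide middle group (cuts at 14 and 17) does worse: 0.673 + 0.009 + 0.748 = 1.431. Kept: 0.729, so 27% is lost.

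These three-group figures assume the groups are used to test a trend; an unordered two-degree-of-freedom comparison would spend more power.

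**Sensitivity to the age distribution.** An untruncated normal split at the median keeps 2/π = 0.637 (36% lost). Whole-year ages 12–18 fitted to the same mean and SD lose 30% when split at 16 and over, and 13–20% with three groups. A uniform age split at its median loses 25%.

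**Power.** Suppose a continuous Condition × age test had 80% power at two-sided 5% (both assumed, not in the documents). After grouping, power is Φ((1.96 + 0.84)√r² − 1.96): 59% at r² = 0.611 and 62% at r² = 0.661. A simulation with 140 clients and normal age gave 79.5% for continuous age and 60.9% for a median split.

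**The case against.** The strongest reply is that subgroups is loose wording. It closes a list of three factors, two of them categorical, and the research question itself does not use the word. Where the plan does intend to split a variable it says so, as with SU+ and SU− and with high versus low or no medication use. On that reading nothing is discarded and only the coding of age is missing. This has force as a reading of intent, but it does not remove the problem, because no other part of the document specifies a continuous age test. An analyst holding only this text would form groups.

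Two stronger readings are tempting, and the documents support neither.

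- A reader might infer that the plan contradicts itself, using age as continuous in the main models and then cutting it. The covariate statement ("all models will be adjusted for nuisance covariates: sex, age, and ethnicity") gives no coding, so no such contradiction can be shown.
- A reader might infer a fixed loss, such as about a third. That figure assumes two groups cut near the centre, which the plan never states.

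It is also fair to say that the stakes are modest. The plan describes this step as further exploration, after the Condition × substance use test, and the information loss as calculated applies only if the age trend is roughly linear.

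**Conclusion.** The concern holds as a gap in specification with a clearly better alternative. The method given for age is subgrouping, with the cut points, number of groups and Condition × age term all unstated, for a variable that is available as a number. Under roughly normal age and roughly linear modification, the loss runs from about 18–20% for three reasonably balanced groups, through 34–39% for one cut between 15 and 16, to 53–61% for one cut at 17 or 14. The size rests on those assumptions and cannot be narrowed from the documents. That the cut could be chosen after seeing the data does not depend on them.

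This is a cheap improvement to an exploratory analysis. It does not touch the Aim 1 comparison of conditions or the Condition × substance use test.

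**What to change.** In Plan of Analysis for Main Outcomes: Aims 1 & 3, replace the age part of the subgroup sentence with the following:

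- Enter age at baseline in years as a continuous variable, and say so.
- Test heterogeneity by age through a Condition × age effect on the growth slope. Naming the interaction matters, because a main effect of age alone would not test heterogeneity of the treatment effect.
- Check linearity by adding one quadratic age term to that interaction model.
- Report the fitted treatment effect with its confidence interval at two or three ages stated in advance, for example 13, 15 and 17.
- Use any age groups for display only, with cut points fixed in advance.

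Sex and ethnicity can stay as categories. The cost is wording alone: no new data, procedures or clients. The small downside is the assumption of a roughly linear age trend, and with 140 clients the quadratic check will detect only marked curvature.
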